5.5.12.1.6. Immunogenicity

The summary TFLs will be based on 6 arms (LY120/LY120, LY240/LY240, PLA/LY120, PLA/LY240, CM120, CM240). To evaluate the changes in immunogenicity data of

- Anti-LY2951742 Antibody (hereafter, “Anti-Drug Antibody (ADA),”)
- Neutralizing ADA (hereafter, “Neutralizing Antibody” (NAb)) after treatment,

the statistical analyses (Fisher's exact test) are planned for comparison between treatment groups.

The summary (baseline=Visit 3) will be created for

1. SP III (safety population)
2. SP III (ADA follow-up cohort)
3. SP III and SP IV combined (ADA follow-up cohort)

Analysis of each period includes:

- The incidence of “ADA positive (%)” and “ADA positive and NAb Positive (%)” during baseline.
- The incidence of treatment emergent ADA (TE ADA) between treatment groups. The baseline and post-baseline definitions for each study period is shown in [Table CGAP. 5.4](#). Treatment emergent ADA will be defined as any of the following:
 - A negative baseline result and a positive post-baseline ADA result with a titer ≥ 20 . This is also called treatment-induced ADA.
 - A positive baseline result and a positive post-baseline ADA result with a ≥ 4 -fold increase in titers (for example, baseline titer of 10 increasing to ≥ 40 post-baseline). This is called treatment-boosted ADA.
- The incidence of TE-ADA and NAb Positive combined.

Note that TE-ADA can happen at multiple visits during SP III (or SP III and SP IV combined) because the judgement is solely based on comparison between the particular visit and the baseline. (i.e., listings may contain multiple TE-ADA time points, although one TE-ADA point is enough to be considered being TE-ADA subject with that TE-ADA.)

The following will also be created:

- Listing of subjects with TE-ADA at any time during study (SP III and SP IV combined), NAb Status will also be displayed.
- Listing of subjects with ADA detected at any time during study (SP III and SP IV combined) excluding subjects with TE-ADA.
- Listing of subjects with TEAEs of hypersensitivity reactions or injection site reactions or ADA present at any time (SP III, SP IV).

5.5.12.2. Continuous Safety Measures

Analyses of continuous safety data will be conducted on safety patients who have a baseline and at least one post-baseline observation for each analysis period (SP III, SP IV, SPIII and SP IV combined).

When mixed model repeated measures analysis is used, values from unscheduled visits will be ignored and only value collected at scheduled visit will be used.

For the following continuous safety measures, changes from last baseline value to LOCF endpoint will be assessed using an ANCOVA model as described in Section 5.5.1.1 with the fixed categorical effects of treatment, baseline value as the covariate:

- laboratory for SP III
- laboratory for SP IV
- weight for SP III
- ECG for SP III
- ECG for SP IV

If repeat laboratory values, weight or ECG exist at the same scheduled visit, only the last nonmissing value at a visit (selected by using the variable with highest lab sequence ID) will be used in the ANCOVA analysis for mean change from the last baseline value to LOCF endpoint.

For the following safety measures, the mean change from baseline will be analyzed using a mixed model repeated measures analysis. The analysis will include the fixed categorical effects of treatment, month and treatment-by-month interaction, as well as the continuous fixed covariates of baseline value and baseline-by-month interaction:

- vitals (SBP, DBP, Pulse) for SP III
- vitals (SBP, DBP, Pulse) for SP III and SP IV combined (safety population)
- weight for SP III and SP IV combined (safety population)
- temperature for SP III
- temperature for SP III and SP IV combined (safety population)

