Abbreviations: CGRP = Calcitonin-gene related peptide; CRP = Lilly Clinical Research Physician; CRS = Lilly Clinical Research Scientist; C-SSRS = Columbia Suicide Severity Rating Scale; D14 = Day 14; DNA = deoxyribonucleic acid; ECG = electrocardiogram; ET = early termination; FSH = follicle stimulating hormone; HbA1c = glycated haemoglobin; HCRU = Health Care Resource Utilization; MIDAS = Migraine Disability Assessment test; MSQ (v2.1) = Migraine Specific Quality of Life Questionnaire; PGI-I = Patient Global Impression of Improvement; PGI-S = Patient Global Impression of Severity; PK = pharmacokinetics; PSMQ-M = Participant Satisfaction with Medication Questionnaire-Modified; RNA = ribonucleic acid; SP = Study Period; SHSF = Self-harm supplement form; SHFU = Self-harm follow-up form.

Note: Selected tests may be obtained in the event of a treatment-emergent hepatic abnormality and follow-up may be required with patients in consultation with the Lilly, or its designee (CRP/CRS). See Appendix 4 of the protocol for more details regarding specific hepatic monitoring tests. If the patient has discontinued the trial and returns for hepatic follow-up, the site should use the 800 series as the visit designation.

- ^a The eligibility period of the prospective baseline assessment will last from 30 to 40 days. Investigators and patients may have up to an additional 5 days to schedule their Visit 3 appointment (beyond the 40 days); however, eligibility will be based on the 30-40 day period.
- b Physical examinations at screening must include a neurological exam.
- ^c Electrocardiograms as single, 12-lead digital will be performed at Visit 1, Visit 3, Visit 10, Visit 16, and Visit 18 or early termination. Note: The Visit 3 ECG should be collected prior to blood draws and dosing. Patients must be supine for approximately 5 to 10 minutes before ECG collection and remain supine but awake during ECG collection. For screening only, ECG results will be read locally.
- Vital signs will include body temperature, blood pressure, and pulse. Blood pressure and pulse will be measured in triplicate in the sitting position and should be measured prior to blood draws. Blood pressure will be assessed by utilizing a calibrated machine.

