5.2. Determination of Sample Size

Approximately 300 patients (approximately 150 patients per arm; approximately 240 patients with EM and approximately 60 patients with CM) will be enrolled for the purposes of regulatory registration, to ensure at least 100 patients per arm with 1 year of exposure. It is assumed that 30% of patients will not complete a 12-month treatment period.

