For safety analysis, when statistical model is used such as MMRM, or ANCOVA, then 4 arms (EM120, EM240, CM120, CM240) will be used without any statistical comparisons between arms.

For listings, they will be displayed by 6 arms (LY120/LY120, LY240/LY240, PLA/LY120, PLA/LY240, CM120, CM240), unless otherwise specified.

All statistical tests will be conducted at a 2-sided alpha level of 0.05, and 95% confidence intervals will be provided, if appropriate. No adjustments for multiplicity will be applied to any safety or effectiveness analyses.

Change from baseline of continuous variables with repeated measures will be analyzed using a mixed model repeated measures (MMRM) analysis, unless otherwise specified. An MMRM analysis refers to a restricted maximum likelihood (REML)-based, mixed-effects repeated measures analysis using all the longitudinal observations at each post-baseline visit.

For other continuous variables without repeated measures, the change from baseline to LOCF endpoint will be analyzed using an analysis of variance (ANOVA) or ANCOVA model.

Unless otherwise specified, when an ANOVA model or ANCOVA model is used to analyze a continuous efficacy variable, type III sum-of-squares for the least-squares means (LSMean) will be used for the statistical comparisons.

Visit-wise binary efficacy variables will be analyzed using a generalized linear mixed model (GLIMMIX) as pseudo-likelihood-based mixed effects repeated measures analysis for categorical data (MMRM-CAT).

For categorical efficacy variables without repeated measures, comparisons between treatment groups will be performed using logistic regressions.

For other categorical variables without repeated measures, comparisons between treatment groups will be performed using Fisher's exact tests unless otherwise specified. For example,

- Baseline patient characteristics
- Safety measures (including percentages of patients with TEAEs, SAEs, and AEs reported as a reason for discontinuation, as well as those patients who met categorical criteria for changes in vital signs and weight, ECGs, and laboratory tests)

Only scheduled visit data will be available for the following data. In other words, there will be no unscheduled visit data;

- Patient migraine headache data collected by diary
- PGI-S
- PGI-I
- MSQ v2.1
- MIDAS
- PSMQ-M
- HCRU

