- Estimated Proportion of 75% Responders for Migraine Headache Days by 2 arms (CM120, CM240) using GLIMMIX
- Estimated Proportion of 100% Responders for Migraine Headache Days by 2 arms (CM120, CM240) using GLIMMIX
- Change from Baseline in Migraine-Specific Quality of Life Questionnaire - Role Function-Restrictive Domain Score by 2 arms (CM120, CM240) using MMRM
- Change from Baseline in Patient Global Impression - Severity Scores by 2 arms (CM120, CM240) using MMRM

Safety: AE

- Overview of Adverse Events
- Adverse Events Leading to Discontinuation
- Serious Adverse Events
- Adverse Events Related to Injection Sites Leading to Discontinuation
- Adverse Events Leading to Discontinuation for Upper Respiratory Tract Infections
- Treatment-Emergent Adverse Events Related to Injection Sites by Max Severity
- Treatment-Emergent Adverse Events (sort by Preferred Term)
- Listing of Adverse Events Leading to Discontinuation and Serious Adverse Events

Safety: Lab

- Abnormal Changes in Hepatic Laboratory Measures at Any Time
- Treatment-Emergent Abnormal Laboratory Measures at Any Time
- Listing of Subjects with abnormal Laboratory Results
- Listing of Subjects with abnormal Hepatic Laboratory Results

Safety: ECG

- Shift Table Summary of Qualitative ECG Abnormalities by Finding Category
- Summary of Qualitative ECG Abnormalities - From Baseline Normal to Post-Baseline Abnormal
- Change from Baseline to LOCF Endpoint in ECG Intervals and Heart Rate
- Treatment-Emergent Abnormalities for ECG Intervals and Heart Rate at Any Time
- Listing of Subjects with Treatment or Post-Treatment Emergent ECG findings
- Listing of Subjects with QRS ≥ 120 Milliseconds at Any Time
- Listing of Abnormal Qualitative ECG by Finding Category

Safety: Other

- C-SSRS summary and/or listing

Protocol Deviations

- Summary of Important Protocol Deviations in SP III
- Summary of Important Protocol Deviations in SP IV
- Listing of Important Protocol Deviations in SP III
- Listing of Important Protocol Deviations in SP IV

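### SP III laboratory and ECG mean changes get only an LOCF ANCOVA, so a one-year safety result mixes times on treatment and shows no time course

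*SAP*

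**What the plan says.** SAP 5.5.1 sets a default: "Change from baseline of continuous variables with repeated measures will be analyzed using a mixed model repeated measures (MMRM) analysis, unless otherwise specified". It then gives the other route: "For other continuous variables without repeated measures, the change from baseline to LOCF endpoint will be analyzed" by ANOVA or ANCOVA.

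SAP 5.5.12.2 divides the continuous safety measures by name. For laboratory (SP III and SP IV), ECG (SP III and SP IV) and SP III weight, "changes from last baseline value to LOCF endpoint will be assessed using an ANCOVA model". Blood pressure, pulse and temperature get an MMRM with treatment, month, treatment-by-month, baseline and baseline-by-month. Weight gets the same MMRM over SP III and IV combined.

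Table CGAP. 5.4 has an LOCF/ANCOVA row for continuous safety only under SP IV. The SP III row lists scheduled visits after Visit 3 up to Visit 16 and gives no last-observation rule.

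On dropout, SAP 5.2 states: "It is assumed that 30% of patients will not complete a 12-month treatment period". On ECG timing, the protocol addendum's Schedule of Activities states: "Electrocardiograms as single, 12-lead digital will be performed at Visit 1, Visit 3, Visit 10, Visit 16, and Visit 18 or early termination". The interim report list in SAP 5.8.1 includes "Change from Baseline to LOCF Endpoint in ECG Intervals and Heart Rate".

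**The concern.** The primary objective in Table CGAP. 4.1 is safety and tolerability over one year of treatment, and ECGs and laboratory measures are named endpoints. The arms are two doses of the same drug, and SAP 5.5.1 has the safety models make no between-arm comparison. The mean change within an arm is therefore what will be read.

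In the CM schedule the Month 12 visit is also the early-termination visit. The LOCF endpoint of someone who leaves in Month 2 is a Month 2 value, and it is averaged with Month 12 values as if they were alike. The mean belongs to no fixed time, and the analysis shows neither when a shift began nor whether it was still growing. A slow drift in a laboratory value or in QTc would look smaller than it is at one year. SAP 5.5.12.2 already contains a model that avoids this for other vital measures, and it gives no reason for treating laboratory and ECG means differently.

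**Working it through.** **Inputs from the documents**
- Size and non-completion (SAP 5.2): about 150 patients per arm, 30% not completing 12 months.
- SP III post-baseline visits (protocol addendum, CM schedule): haematology and chemistry at Visits 7, 10, 13 and 16/ET (Months 3, 6, 9, 12); HbA1c, urinalysis, ECG and weight at Visits 10 and 16/ET (Months 6, 12).
- SP IV: one scheduled laboratory and ECG visit (Visit 18/ET).

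**Assumptions, not in the documents:** the shape of any drift, when patients leave, and that a value is taken at leaving.

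**1. The plan's own figure.** 150 × (1 − 0.30) = 105 per arm, which meets the aim "to ensure at least 100 patients per arm with 1 year of exposure". The plan thus allows for 150 × 0.30 = 45 patients per arm without a Month 12 value on treatment.

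**2. Are these repeated measures?** In SP III, yes: four post-baseline visits for haematology and chemistry, two for ECG and HbA1c. In SP IV, no.

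**3. Expected LOCF mean.** Let d be the non-completion proportion, f(t) the mean change at month t, and T a leaver's time of leaving. Then

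LOCF mean / Month 12 mean = (1 − d) + d × E[f(T)] / f(12).

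With d = 0.30 and a value at leaving:

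| Drift | Leaving | E[f(T)]/f(12) | Ratio | Understated by |
|---|---|---|---|---|
| Linear | Even | 0.50 | 0.70 + 0.30 × 0.50 = 0.85 | 15% |
| Linear | Early (mean at 1/3 of the year) | 0.333 | 0.80 | 20% |
| Linear | Late (mean at 2/3 of the year) | 0.667 | 0.90 | 10% |
| Accelerating (quadratic) | Even | 0.333 | 0.80 | 20% |
| Plateau, time constant 3 months | Even | 0.769 | 0.931 | 6.9% |
| Plateau, time constant 1.5 months | Even | 0.875 | 0.963 | 3.7% |

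The table departs from the linear, even-leaving case one assumption at a time. Combining them widens the span: 0.9% for the faster plateau with late leaving, 24% for accelerating drift with early leaving.

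With linear drift and even leaving the understatement is d × 0.5: 5% at d = 0.10 and 10% at d = 0.20.

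**4. No value at leaving (linear, even, d = 0.30).**
- Haematology and chemistry: leavers before Month 3 (0.30 × 0.25 = 7.5% of patients) drop out; the others average 0.5. (0.70 + 0.225 × 0.5) / 0.925 = 0.878, so 12.2%.
- ECG: leavers before Month 6 (15%) drop out; the others contribute Month 6. (0.70 + 0.15 × 0.5) / 0.85 = 0.912, so 8.8%.

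**5. Would a repeated-measures analysis remove it?** In a simulation (150 patients, 2,000 runs, linear drift, 30% leaving evenly and unrelated to outcome), LOCF gave 0.85 of the true Month 12 change. A likelihood estimate from the scheduled Month 6 and 12 values gave 1.00.

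**6. Leavers who drift faster.** At twice the slope, LOCF gives 0.70 + 0.30 × 0.5 × 2 = 1.00 against a true 0.70 + 0.30 × 2 = 1.30, which is 23% low.

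**7. Interim.** By SAP 5.8.1, every randomized patient will have had the chance to reach Month 6, and safety uses all SP III data. Early leavers apart, a patient's last ECG is at Month 6 or Month 12 according to enrolment date. Under linear drift a Month 6 value carries 6/12, or half, of the one-year shift. The documents do not give the mix.

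**The case against.** Much can be said for the plan, and several stronger readings fail.

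- **A reader might infer that the SAP contradicts itself.** It does not. The MMRM default carries an exception clause, and 5.5.12.2 is the named exception. What remains is that no reason is given.
- **A reader might take 15% as the bias.** It is one scenario. Protocol addendum 5.4 equates 5 months with about 5 half-lives, so the half-life is about 1 month and the time constant 1/ln 2, about 1.4 months. If changes follow exposure, the 3.7% row is the closest. EM patients who stay on active drug also have their baseline at CGAP Visit 3, after earlier treatment, which makes a linear rise from baseline less plausible for them.
- **A reader might count SP IV and weight as gaps.** SP IV has one scheduled laboratory and ECG visit, so ANCOVA fits the general rule. Weight already has the SP III/IV MMRM, which can give a Month 12 estimate.
- **A reader might infer that dose comparisons are biased or abnormal values missed.** The safety models make no between-arm contrast. The any-time analyses (treatment-emergent high and low laboratory values, hepatic multiples, QTc thresholds and increases) do not use LOCF. They do, however, detect threshold crossings and not a shift in the mean.
- **The SAP calls the result an LOCF endpoint, never a one-year change.** True, but no other laboratory or ECG mean is specified to answer the one-year question.
- **The interim point is narrow.** Only the ECG table is listed with an LOCF endpoint, and the mixed follow-up is stated openly.
- **MMRM alone is not enough.** Early-termination values share the Visit 16 column. Coded as Month 12, they would carry the same problem into the MMRM. This stands and shapes the fix.

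The schedule supplied covers only CM patients, about 60 of 300. The EM schedule could not be checked.

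**Conclusion.** The point holds for SP III laboratory and ECG means: they are repeated measures (on the CM schedule) summarised only at an LOCF endpoint. That yields a mean at mixed times and no time course for a one-year safety objective. It is a permitted choice that can be improved, not an error.

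At 30% non-completion with values taken at leaving, a progressive shift is understated by about 4% (fast plateau) to 20% (early leaving or accelerating drift), and by 15% with linear drift and even leaving. The 30% is a planning assumption; drift shape and leaving times are this review's assumptions. The effect is confined to within-arm means. This is a cheap improvement.

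**What to change.** - In SAP 5.5.12.2, add the MMRM already written there for SP III laboratory and ECG, and report least-squares means per arm by visit and at Month 12.
- Assign early-termination values to the scheduled month nearest their actual date, not to Month 12. State what happens to a value that lies nearer to baseline than to the first scheduled visit; this matters most for ECG, where that visit is Month 6.
- For weight, report the Month 12 estimate from the existing SP III/IV MMRM.
- Keep the LOCF ANCOVA as supporting, labelled as change to last observation, in the interim ECG table too.

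The cost is more output from a model already specified, plus one visit-mapping rule. The MMRM relies on data missing at random, which is doubtful if abnormal results prompt leaving; keeping the LOCF table alongside lets a reader see whether the two differ.

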5.5.13. Subgroup Analyses

Some TFLs listed below for patients with self-injection experience will be created for 4 arms (EM120, EM240, CM120, CM240).

Efficacy/ health outcome measures (descriptive summary):

- Mean change from baseline (Visit 3) in the number of migraine headache days (Table)
- Mean change from baseline (Visit 3) in the number of migraine headache days (Figure)
- Mean change from baseline in the number of headache days
- Mean change from baseline in the number of monthly migraine headache days requiring medication for the acute treatment of migraine headache
- Treatment Compliance

- PSMQ-M summary

AE related summary:

- Duration of Treatment-Emergent Adverse Events Related to Injection Sites (Figure)
- Duration of Treatment-Emergent Adverse Events Related to Hypersensitivity Events (Figure)
- Treatment-Emergent Adverse Events Related to Injection Sites by PT
- Treatment-Emergent Adverse Events Related to Injection Sites by Max Severity by PT
- Treatment-Emergent Hypersensitivity Events by PT
- Treatment-Emergent Hypersensitivity Events by Max severity by PT
- Treatment-Emergent Adverse Events by PT
- Treatment-Emergent Adverse Events by Max Severity by PT
- Listing of Adverse Events Leading to Discontinuation and Serious Adverse Events
- Listing of Subjects with Treatment-Emergent or Post-Treatment Emergent Adverse Events

Demographics:

- Baseline Demographics and Disease Characteristics - Continuous Variables
- Baseline Demographics and Disease Characteristics - Categorical Variables

5.6. Interim Analyses

At least 1 interim analysis is planned after the database lock for Study CGAN. The interim analysis will be conducted to support regulatory submission prior to all patients completing the CGAP study.

5.7. Unblinding Plan

CGAP is an open label study. However EM patients' injection at CGAP Visit 3 will be kept blind until the earliest timing of an interim CGAN database lock (DBL) (if it takes place), the final CGAN DBL, or the interim CGAP DBL (if it takes place).

The earliest timing of the interim CGAP DBL (if it takes place) or the final CGAP DBL will be equal to or later than the earliest timing of the interim CGAN DBL (if it takes place) or the final CGAN DBL. This guarantees that all CGAN patients finish the CGAN double blind treatment period (Study Period III) and the data in CGAN Study Period III is locked.

When the interim CGAN DBL, the final CGAN DBL, or the interim CGAP DBL takes place, then an unblinding occurs. The unblinding will reveal the CGAP Visit 3 injection, as well as CGAN treatment arms for EM patients.

During the CGAP study, some members are unblinded ([Table CGAP. 5.8](#)). They do not have direct interaction with sites. They will not be allowed to join meetings which may affect the

other members' blind condition, such as trail level safety review (TLSR) and data review meetings.

Table CGAP. 5.8 Unblinded Members through CGAP Study

Role	Reason	Data source for unblinding
Product Delivery personnel	To provide and manage Clinical trial materials	e-CTS
Clinical Laboratory Operations	To manage and track sample shipping	CLRM
Unblind Case Manager	To report SAE with unblinded information to EU authority	e-CTS
Data Movement	To transfer unblinded data at the timing of the interim CGAN DBL, the final CGAN DBL, or the CGAP interim DBL	source data of CLUWE

Abbreviations: CLRM = Clinical Laboratory Results Modernization; DBL = database lock; e-CTS = Enhanced Clinical Trials System; EU = European Union; GPS = Global Patient Safety; IWRS = interactive web-response system; PK/PD = pharmacokinetics/ pharmacodynamics; SAE = Serious Adverse Event.

The CGAP interim analysis will be conducted by the CGAP unblinded study members. They do not have direct interaction with sites ([Table CGAP. 5.9](#)) after the unblinding. These members will become unblinded after the earliest timing of the interim CGAN DBL, the final CGAN DBL, or the CGAP interim DBL. All study personnel with direct interaction with sites after the unblinding are kept blinded to the interim analysis results.

Table CGAP. 5.9 Unblinded Members Unblinded after the Earliest Timing of the Interim CGAN DBL, the Final CGAN DBL, or the CGAP Interim DBL

Role	Reason	Data source for unblinding
Project Statistician	CSR/PMDA consultation preparation	CLUWE/TFL
Statistical Analyst	CSR/PMDA consultation preparation	CLUWE/TFL
Statistical Analysis programmers	CSR/PMDA consultation preparation	CLUWE/TFL
Medicals (Clinical Research Scientist, Clinical Research Physician)	CSR/PMDA consultation preparation	TFL
PK/PD	CSR/PMDA consultation preparation	CLUWE/TFL
Medical Writer	CSR/PMDA consultation preparation	TFL
CPM	CSR/PMDA consultation	TFL

	preparation	
CTPM	CSR/PMDA consultation preparation	TFL
PPM	CSR/PMDA consultation preparation	TFL
Regulatory	CSR/PMDA consultation preparation	TFL
Data Management	CSR/PMDA consultation preparation	CLUWE/TFL

Abbreviations: CPM = Clinical Project Manager; CTPM = Clinical Trial Project Manager; CSR = Clinical Study Report; TFL = tables, figures, listings; PK/PD = pharmacokinetics/pharmacodynamics; PPM = Product Project Manager; CLUWE = Clinical Users Working Environment;

